## 11.3. Efficacy Analyses

### 11.3.1. Analysis of the Primary Endpoint

The primary objective of this study is to test the hypothesis that either dose regimen evaluated for atabecestat will slow cognitive decline compared with placebo, as measured by the primary endpoint of the PACC change from baseline at Month 54 (see Section 9.3.1).

The primary estimand, the main clinical quantity of interest to be estimated in the study, is defined by the difference in means versus placebo for the primary endpoint in the specified population under the following postrandomization measure of intervention:

- **Population:** amyloid-positive subjects who are asymptomatic at risk for developing Alzheimer's dementia
- **Endpoint:** The Month 54 (Year 4.5) PACC change score (as defined in Section 9.3.1)
- **Measure of Intervention:** the effect of the initially randomized treatment regardless of treatment compliance or initiation of any Alzheimer adjunctive therapy.

The primary analysis will be based on the intent-to-treat analysis set, which includes all randomized subjects. The analysis of the PACC change score will only include subjects for whom the PACC change score is non-missing at least 1 postbaseline time point. Measurements collected after initiation of any Alzheimer adjunctive therapy will be included in the analysis for the primary estimand. Measurements collected after treatment discontinuations due to reasons potentially related to treatment (eg, treatment-related adverse events or lack of efficacy) will also be included in the analysis of the primary estimand. However, measurements collected after treatment discontinuations due to events that are clearly not treatment-related (eg, life events such as relocation, loss of transportation, loss of informant) will not be included in the analysis of the primary estimand.

A mixed effect model for repeated measurement (MMRM) analysis will be performed to assess the treatment effect. The change from baseline in PACC at each visit that the endpoint is measured will be the dependent variable. Visits scheduled for the measure will be treated as a categorical variable with values equal to the visit numbers. An unstructured covariance structure will be assumed. The model for the fixed effects will include the following terms: baseline of the endpoint measure, treatment group, visit, treatment-by-visit interaction, age, sex, education, hippocampal volume, country, and *APOE*  $\epsilon 4$  carrier status.

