1. INTRODUCTION

This statistical analysis plan (SAP) contains definitions of analysis populations, derived variables and statistical methods for the analysis of efficacy and safety for study 54861911ALZ2003.

Screening, randomization, and dosing in this study was stopped on 17 May 2018. Randomized subjects were to continue in the double-blind treatment phase without treatment (as allowed by protocol) for approximately 3 to 6 months from cessation of dosing. This permitted continued safety monitoring of the subjects per protocol. The planned last-patient-out date is 17 September 2018, except for some subjects who may require further follow-up.

At the time of cessation of screening and randomization, 557 (34%) subjects of the planned 1650 had been randomized. The planned duration of treatment was 54 months. As of the time of cessation of dosing, no subject had more than 27 months of treatment and 447 had 12 months of treatment or less.

As a result of the significantly reduced sample size, the objectives of the study as stated in the protocol and in Section 1.1 below cannot be evaluated. Safety outcomes will be summarized with descriptive statistics. The planned interim analysis of CSF A β ₁₋₄₀ was performed but other planned interim analyses will not be performed. Between-group comparisons of selected efficacy outcomes will be performed. Other efficacy outcomes will be summarized with descriptive statistics

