5.2.3. Analysis Methods

The primary analysis is based on the primary analysis set defined in Section 5.2.1 and uses an MMRM model. This relies on the Missing at Random (MAR) assumption: after accounting in the model for the effects of the covariates and for the available efficacy scores, the unobserved data have the same distribution as the observed data.

The PACC change score will be analyzed by an MMRM model based on observed data at on-treatment visits. The fixed terms for this model are treatment group, sex, country, APOE ε4 carrier status, education level, PACC baseline score, age at study entry, average hippocampal volume at baseline, time point (as a factor), and the interaction of treatment and time point. Subject is included as a random effect.

Comparisons between each atabecestat dose group and placebo will be performed at Months 6, 12, and 18 by using the appropriate contrasts based on this model. The Kenward-Roger approximation will be used to estimate the denominator degrees of freedom. Between-treatment differences in LS Means with the corresponding 95% confidence intervals (CIs) and p-values will be provided. If the unstructured covariance matrix results in a lack of convergence, starting values will be supplied using estimates from simpler structures. If this strategy does not result in

convergence then the following structures will be used in sequence: heterogeneous autoregressive of order 1 (ARH(1)), heterogeneous compound symmetry (CSH), and homogeneous compound symmetry (CS).

Plots of mean (\pm SE) PACC change score over time by treatment group will be provided for observed data and for estimates based on the MMRM.

For the off-treatment period, change of PACC and the components from off-treatment baseline will be summarized.

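### SAP 5.2.3 pairs a random subject effect with an unstructured covariance; read literally, one covariance parameter is redundant and could set off the convergence fallback for no data reason (low severity)

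*SAP*

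**What the plan says.** **SAP 5.2.3 (PACC change score).** After the fixed terms, which include "time point (as a factor), and the interaction of treatment and time point", the SAP says "Subject is included as a random effect". It then treats an unstructured matrix as the first choice: "If the unstructured covariance matrix results in a lack of convergence, starting values will be supplied using estimates from simpler structures". If that fails, ARH(1), CSH and CS are tried in that order. "Comparisons between each atabecestat dose group and placebo will be performed at Months 6, 12, and 18", and "The Kenward-Roger approximation will be used to estimate the denominator degrees of freedom".

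**Protocol 11.3.1.** For the same endpoint, "An unstructured covariance structure will be assumed", and the model lists fixed effects only. The random subject term therefore enters with the SAP.

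**Reuse.** SAP 5.3.2 applies the same approach to the subject-reported CFI. SAP 5.4.2 applies a similar model, not the identical one, to the PACC components, RBANS scores, informant-reported CFI and ADCS-ADL-PI totals, with time as a continuous variable where visits are unequally spaced.

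**Follow-up available.** SAP 1 reports that "no subject had more than 27 months of treatment and 447 had 12 months of treatment or less".

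The SAP does not say whether the unstructured matrix is the residual matrix, nor that the subject term is dropped when that matrix is used.

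**The concern.** In a mixed model, a random subject intercept adds a common variance to every element of a subject's covariance matrix. An unstructured matrix already has a free parameter for each of those elements, so the data cannot separate the two. The redundancy is algebraic, holds for any data set, and is not removed by new starting values, which are the SAP's first remedy.

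This matters because the SAP lets convergence choose the covariance structure. A redundant parameter can give a singular Hessian or a convergence failure. A programmer following the rule would read that as failure of the unstructured matrix and move on to ARH(1), CSH or CS. The reported intervals and p-values could then rest on a more restrictive covariance because of how the model was written and not because of the data. Two programmers could also read the sentence differently and fit different models.

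**Working it through.** The plan gives no figure on this point to reproduce. The check counts parameters against what can be identified, then looks at whether estimates move.

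**Inputs.**
- Visits, PACC: scheduled every 6 months (SAP 5.2.2). With no subject beyond 27 months, at most Months 6, 12, 18 and 24 are available, so T = 4. The comparisons use T = 3.
- Visits, CFI: scheduled annually after randomization (SAP 5.3.1). Within 27 months that is Months 12 and 24, so T = 2.
- Structures: unstructured (UN), ARH(1), CSH, CS (SAP 5.2.3).

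**Algebra.** The marginal covariance is V = σ_b²·J + R, where J is the T × T matrix of ones and R is the within-subject matrix.
- UN: replace σ_b² by σ_b² + δ and R by R − δJ. V is unchanged for any δ that keeps σ_b² non-negative and R positive definite. R has T(T+1)/2 parameters and V has T(T+1)/2 distinct elements, so the intercept is always one too many.
- CS: R = aJ + bI gives V = (σ_b² + a)J + bI. Only the sum σ_b² + a can be estimated.

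**Parameter count and rank** of the derivative of V with respect to its parameters, with the random subject effect included:

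| Structure | T = 2 | T = 3 | T = 4 |
|---|---|---|---|
| UN | 4, rank 3 | 7, rank 6 | 11, rank 10 |
| ARH(1) | 4, rank 3 | 5, rank 5 | 6, rank 6 |
| CSH | 4, rank 3 | 5, rank 5 | 6, rank 6 |
| CS | 3, rank 2 | 3, rank 2 | 3, rank 2 |

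CSH is full rank at T = 3 and 4 only when the visit variances differ. At T = 2 the result follows by counting: V has 3 distinct elements, while UN, ARH(1) and CSH each carry 3 parameters plus the intercept. So for PACC the first and last structures are redundant, and for the CFI all four are.

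**Without the random effect.** UN is fully identified: 6 parameters, rank 6 at T = 3; 10, rank 10 at T = 4.

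**Do the estimates move?** One data set was simulated with 557 subjects (the number randomized, SAP 1), three arms and four visits. Assumed: SDs 1.8, 2.0, 2.2 and 2.44, correlation 0.5, and 40/40/15/5% of subjects with 1/2/3/4 visits. The first two shares sum to 80%, in line with 447/557 = 80.3% having 12 months of treatment or less. The fitted mean model had treatment-by-visit terms only. R was unstructured and σ_b² was fixed in turn at 0, 0.25, 0.5, 1.0 and 1.4.
- −2 REML log-likelihood, up to a constant: 2247.5301 at every value.
- 25 mg versus placebo at the first three visits: 0.2293, 0.2848, 0.6649 at every value.
- Model-based standard errors: 0.1848, 0.2512, 0.3978 at every value.

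The likelihood is flat in that direction, and the contrasts and model-based standard errors do not depend on where along it the fit stops. Kenward-Roger degrees of freedom were not computed. They use the information matrix of the covariance parameters, which is singular here, so their behaviour would depend on the software.

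**The case against.** The strongest reply is that the SAP may not specify this model at all. It calls the analysis an MMRM, names a single covariance matrix, and offers the fallbacks as alternatives to that one matrix. It describes no separate random-effect variance. On that reading the sentence loosely says that subject is the clustering unit, the model matches the protocol, and there is no defect. This is plausible and cannot be excluded, but the SAP does not state it, and the literal wording gives a different model.

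The second reply is that little follows even on the literal reading. V stays identified, and V determines the contrasts. That stands for UN, as the simulation shows, and for CS by the same algebra, since CS plus an intercept is still CS. Flatness also does not imply non-convergence: software may set the subject variance to zero or settle on an arbitrary split.

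A reader might therefore infer more than is supported: that the unstructured and CS models cannot be estimated properly, that the treatment estimates are biased, or that the fallback will be triggered. None of these is shown. Nor do all secondary endpoints use the identical model; SAP 5.4.2 says only that it is similar. No shift in standard errors from an unnecessary fallback has been quantified.

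**Conclusion.** The point holds as a specification error of low severity. Taken literally, the SAP model has exactly one redundant covariance parameter under UN and under CS for PACC, and under all four structures for the subject-reported CFI at its two scheduled on-treatment visits. For the CFI, no step in the sequence is then identified.

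If the fit converges under UN, the contrasts and model-based standard errors are those of the protocol's model. The remaining risk is procedural: a warning or failure produced by the redundant term could move the analysis to a more restrictive structure. Whether that happens depends on the software.

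This rests on reading the sentence as a random intercept added to a within-subject matrix, and on scheduled visits only. Severity is low because SAP 1.3 rules out formal hypothesis testing and SAP 5.1.1 treats every comparison as exploratory. Between-group intervals and p-values will still be reported, so the model should be unambiguous.

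**What to change.** In SAP 5.2.3, delete "Subject is included as a random effect". In its place state that within-subject correlation is modelled only through the covariance matrix of the repeated measures, with subject as the clustering unit, and that no random subject effect is fitted under UN or under any fallback structure. Make clear that this also governs the CFI model (5.3.2) and the similar models in 5.4.2.

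The cost is one sentence. Under UN the change leaves the maximised likelihood and the contrasts as they were, restores full rank, and agrees with Protocol 11.3.1. Under ARH(1) and CSH with three or more visits the subject term is not redundant, so removing it does define a simpler fallback: 4 parameters instead of 5 at three visits, 5 instead of 6 at four. That choice should be made explicitly now and not left to the programmer.

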5.2.3.1. Subgroup Analyses

Certain subgroups of subjects, based on their baseline clinical presentation, may be more sensitive to a treatment effect than the population as a whole. PACC change score will be summarized in the following subgroups:

- APOE ϵ 4 carriers
- APOE ϵ 4 non-carriers

In addition, the PACC change score will also be summarized across various other subgroups of subjects (as defined in Section 2.7)

5.3. Key Secondary Endpoint

5.3.1. Definition

The key secondary efficacy endpoint is the change from baseline in the subject-reported Cognitive Function Index (CFI) total score. The CFI is a modified version of the Mail-in Cognitive Function Screening Instrument²⁰, a subject- and informant-reported outcome measure developed by the ADCS. The subject-reported and informant-reported CFIs are assessed on the same schedule: 5 to 10 days before randomization, then annually after randomization through Month 48, and at Month 54 (or early termination if not performed at previous visit). This assessment includes 14 questions that assess the subject's perceived ability to perform high-level functional tasks in daily life and sense of overall cognitive functional ability (yes=1; no/does not apply=0; maybe=0.5 for each question) and 1 additional question about whether the subject has seen a doctor in the last year about memory concerns. Study subjects and their informants independently rate the subject's abilities.

The CFI total score is the sum of the first 14 questions, with higher scores indicating greater impairment (range = 0 to 14). If there are fewer than 5 (<30%) missing items, an imputed total score will be calculated as a prorated total based on the observed items:

$$14 * \left(\frac{\text{Total score of non-missing items}}{\text{Total number of non-missing items}} \right)$$

Imputed total scores will be rounded to 1 decimal place. If there are 5 or more missing items, the total score will be missing. A subject-reported and an informant-reported total score will be calculated. Change from baseline in the CFI total score will be calculated at each time point. For off-treatment visits, change from the off-treatment baseline (see Section 2.4) will also be calculated.

5.3.2. Analysis Methods

Change from baseline in subject-reported CFI total score in the on-treatment period will be analyzed using the same MMRM approach as described for the primary efficacy endpoint in Section 5.2.3. For off-treatment visits, change from off-treatment baseline will be summarized. If the recall period of an off-treatment CFI assessment overlapped with the on-treatment period, then the score will be excluded from the off-treatment summary.

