2.4. Visit Windows

As subjects do not always adhere to the protocol visit schedule, the following rules are applied to assign actual visits to analysis visits. Listed below are the visit windows and the target days for each visit. The same definitions will apply to visits before or after the treatment end date using the Analysis Day as defined in Section 2.3 above. The time period description will be appended with '(On-Trt)' for post-baseline visits on or prior to the treatment end date. The time period description will be appended with '(Off-Trt)' for post-baseline visits after the treatment end date. If a subject has 2 or more actual visits in one visit window, the visit closest to the target day will be used as the protocol visit for that visit window. The other additional visit(s) will not be used in the summaries or analyses but they can be used for determination of clinically important endpoints. If 2 actual visits are equidistant from the target day within a visit window, the later visit will be used.

All assignments will be made in chronological order. Once a visit date is assigned to a visit window, it will no longer be used for a later time point except for the endpoint. Listed below (Table 1) are the visit windows and the target days for each visit defined in the protocol.

Table 1: Visit Windows for on and off-treatment Analysis

Scheduled Visit Number	Time period (label on output)	Time Interval (Day*)	Target Time Point (Day)
7	Baseline	-120 to 1	1
8	Week 2	2 to 22	15
9	Week 4	23 to 36	29
10	Week 6	37 to 50	43
11	Week 8	51 to 64	57
12	Week 10	65 to 81	71
13	Month 3	82 to 106	92
14	Month 4	107 to 134	120
15	Month 5	135 to 165	148
16	Month 6	166 to 211	183
17	Month 8	212 to 256	239
18	Month 9	257 to 288	274
19	Month 10	289 to 333	302
20	Month 12	334 to 410	365
21	Month 15	411 to 501	456
22	Month 18	502 to 592	547
23	Month 21	593 to 683	638
24	Month 24	684 to 774	729
25	Month 27	775 to 865	820
26	Month 30	866 to 956	911
27	Month 33	957 to 1047	1002
28	Month 36	1048 to 1138	1093
29	Month 39	1139 to 1229	1184
30	Month 42	1230 to 1320	1275
31	Month 45	1321 to 1411	1366
32	Month 48	1412 to 1502	1457
33	Month 51	1503 to 1593	1548
34	Month 54	1594 to 1684	1639
	Month >54	1685 to ∞	1685

* Relative to analysis reference start date if visit date is prior to or on the treatment end date. Relative to treatment end date if visit date is after treatment end date.

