5.4.1.7. ADCS Activities of Daily Living – Prevention Instrument (ADCS-ADL-PI)

The ADCS-ADL-PI is administered 5 to 10 days before randomization, then every 3 months through Month 54 (or early termination if not performed at the previous visit). The ADCS-ADL-PI includes 15 questions related to activities of daily living and 3 questions related to high-level function². High-level function items ask about the use of electronic devices such as cellphones/smartphones, computers/tablets, and e-readers (such as a Kindle or Nook). Study subjects and their informants independently rate the subject’s ability to perform each activity over the past 3 months (with no difficulty = 3, with some difficulty = 2, with a lot of difficulty = 1, did not do/don’t know = 0). Informants are additionally asked to evaluate whether activities were completed less often, required more time to complete, or if any errors were made performing the task. High-level function items are rated as “yes” or “no”.

The ADL total score is the sum of the scores of the 15 activities of daily living questions (range: 0-45) with higher scores indicating less impairment. If there are fewer than 5 (<30%) missing items, an imputed total score will be calculated as a prorated total based on the observed items:

$$15 * \left(\frac{\text{Total score of non-missing items}}{\text{Total number of non-missing items}} \right)$$

Imputed total scores will be rounded to 1 decimal place. If there are 5 or more missing items, the total score will be missing. Both a subject- and informant-reported ADL total score will be calculated. Change from baseline at each time point will be calculated for each activity of daily living (both subject- and informant-reported) and for the subject- and informant-reported ADL total scores. For off-treatment visits, change from the off-treatment baseline (see Section 2.4) will also be calculated.

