5.4.2. Analysis Methods

Analyses of the changes from baseline of each of the 4 PACC components, the changes from baseline of each of the 5 RBANS index scores, the change from baseline of the RBANS Total Scale, changes from baseline in informant-reported CFI total score, and change from baseline in ADCE-ADL-PI total scores (both the subject- and informant-reported) will be performed using a similar MMRM model as described above for the primary efficacy endpoint (Section 5.2.3). For each endpoint, baseline score in the model will be the baseline score for the given endpoint. For endpoints measured at unequally spaced time points, time (month) will be included as a continuous variable. For the individual PACC components, summaries based on both the original and standardized scale will be provided. For off-treatment period, changes from the off-treatment period baseline will be summarized.

For other secondary efficacy endpoints that are continuous parameters, change from baseline at each on-treatment time point will be summarized with descriptive statistics. Inferential analyses may be performed. The distribution of responses to the ADCS-ADL-PI high-level function items will be summarized at each time point by treatment group.

Plots of mean (\pm SE) values and changes over time by treatment group will be provided for selected secondary efficacy endpoints. Change from the off-treatment baseline may also be summarized for each off-treatment time point and plotted.

For Global CDR ≥ 0.5 , the number and percentage of subjects meeting the criterion at any post-baseline on-treatment time point will be summarized. A similar summary based on off-treatment time points may also be provided. Descriptive statistics of the PACC change score may be summarized by treatment group for subjects who did and did not have the Global CDR ≥ 0.5 event at Month 12.

Association between the change from baseline in the CFI subject total score and the PACC change score, the CFI (actual) subject total score and the PACC change score, and the change from baseline in ADCS-ADL-PI subject total score and the PACC change score will be explored. Association between the functional measure and other cognitive measures will be similarly analyzed. Association between the total scores of subject-reported functional measures and the informant-reported functional measures will be explored as well.

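### Off-treatment ADCS-ADL-PI scores carry a 3-month recall that reaches back into dosing, but the SAP applies its recall-overlap exclusion only to the CFI

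*SAP*

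**What the plan says.** SAP 5.3.2 sets a condition for the off-treatment CFI table: "If the recall period of an off-treatment CFI assessment overlapped with the on-treatment period, then the score will be excluded from the off-treatment summary".

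For the ADCS-ADL-PI, SAP 5.4.1.7 has subjects and informants rate the subject's "ability to perform each activity over the past 3 months". The scale is given shortly before randomization, "then every 3 months through Month 54 (or early termination if not performed at the previous visit". The same section adds: "For off-treatment visits, change from the off-treatment baseline (see Section 2.4) will also be calculated".

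SAP 5.4.2 analyses the on-treatment ADCS-ADL-PI totals "using a similar MMRM model as described above for the primary efficacy endpoint (Section 5.2.3", which is the PACC section and not the CFI section. It then states: "For off-treatment period, changes from the off-treatment period baseline will be summarized". Neither section contains a recall condition.

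SAP 2.4 applies the (Off-Trt) label "for post-baseline visits after the treatment end date", with no buffer after the last dose. It defines the off-treatment baseline as the last on-treatment result and End point (Off-Trt) as the last off-treatment result. On follow-up, SAP 1 says: "Randomized subjects were to continue in the double-blind treatment phase without treatment (as allowed by protocol) for approximately 3 to 6 months". It puts planned last-patient-out at 17 September 2018, after dosing stopped on 17 May 2018.

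**The concern.** The CFI rule rests on a sound principle: a score that describes time on drug does not belong in an off-drug table. The ADCS-ADL-PI is also a subject- and informant-reported functional scale. Its recall period is written into the SAP, and it is given every 3 months where the CFI is annual, so it yields more off-treatment records. The principle is nevertheless not applied to it, and no reason is given.

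The off-treatment baseline is itself an on-drug value. A score taken in the first weeks after stopping then largely compares one on-drug period with another, and the difference is tabulated as change off drug. Any decline, recovery or rebound after stopping would look smaller than it was.

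**Working it through.** **Does any other text close the gap?** The CFI rule names only the CFI. SAP 5.4.2 points to 5.2.3, so the rule is not inherited. SAP 2.4 has no buffer. No general rule elsewhere in the SAP or protocol extends the exclusion. The plan states no figure of its own to reproduce here.

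**Overlap by window**
- Recall R = 91 days. This takes 3 months as 13 weeks, the interval in the protocol's visit schedule.
- SAP 2.3 sets off-treatment Analysis Day = visit date − treatment end date + 1, so days since last dose d = Analysis Day − 1. SAP 2.3 also carries a bullet naming the first-dose date as the reference for all later time points; I follow the formula and the Table 1 footnote, which count from the treatment end date.
- On-drug share of recall = max(0, R − d)/R.

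| Off-treatment window | Target day | d | On-drug share |
|---|---|---|---|
| Week 2 | 15 | 14 | 77/91 = 85% |
| Week 4 | 29 | 28 | 63/91 = 69% |
| Week 6 | 43 | 42 | 49/91 = 54% |
| Week 8 | 57 | 56 | 35/91 = 38% |
| Week 10 | 71 | 70 | 21/91 = 23% |
| Month 3 | 92 | 91 | 0/91 = 0% |

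The Month 3 window runs from Day 82 to Day 106. Days 82 to 91 overlap, which is 10 of its 25 days, with a largest share of 10/91 = 11% at Day 82. Month 4 onward is clear. Scheduled visits keep counting from baseline, so a 3-monthly assessment can land in any of these windows.

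**How many scheduled scores overlap**

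This part is an illustrative model; its percentages are not document figures. Assume visits every 91 days with a uniform phase relative to the last dose, and ignore visit windows and early-termination visits. The first off-treatment assessment then falls 0 to 91 days after the last dose, so it essentially always overlaps, with a mean share of 50%. Second and later ones are clear.

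- Follow-up F: 17 May to 17 September 2018 is 123 days, inside the stated 3 to 6 months.
- Share of subjects reaching a second scheduled assessment: (123 − 91)/91 = 32/91 = 35%.
- Share of scheduled off-treatment scores that overlap: 1/(1 + 0.352) = 74%.
- F = 91: no second assessment, so 100% overlap.
- F = 183: every subject has a second and 1/91 have a third, so 1/(1 + 1 + 0.011) = about 50%.

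At F = 123, End point (Off-Trt) would be an overlapping score for the other 59/91 = 65% of subjects.

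**The case against.** The strongest reply is that little depends on this. SAP 5 limits off-treatment efficacy to descriptive statistics, SAP 5.1.1 makes all comparisons exploratory, and SAP 1 concedes that the study objectives cannot be evaluated. That stands, and it caps the importance of the point.

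Second, off-treatment visits are windowed by time since the last dose, so a reader who knows the recall period can discount the early windows. This holds for the windowed rows. It does not hold for End point (Off-Trt), which mixes times since last dose under one label.

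Third, the different treatment may be deliberate. The CFI is annual, and the SAP never states the recall period of its scored items, so the two cases cannot be shown to be equivalent. The CFI-a, rated on current or most recent experience, is less exposed to the problem, though SAP 5.5.2 makes its off-treatment summary optional. All of this is fair, but the SAP gives no reason for the difference, and the ADCS-ADL-PI is the scale whose recall is stated.

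Fourth, outright exclusion would discard most of the data and split the Month 3 window over overlaps of at most 11%. This also stands, and it is why the fix below keeps the early records and flags them.

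A reader might go further and infer that exclusion would cost only a few early records, or that it would empty the table. Neither follows. At 123 days about three-quarters of scheduled scores are affected, but about 35% of subjects keep a clean one. Subjects who stopped drug earlier and stayed in the study (protocol 10.2) can add later clean scores.

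**Conclusion.** The inconsistency is real. As written, the plan reports as off-drug change some ADCS-ADL-PI scores of the kind that its CFI rule would remove. The on-drug share falls from about 85% at the Week 2 target day to 23% at Week 10 and is zero from the Month 3 target day. These shares need only the 91-day reading of 3 months and the Table 1 target days. The statement that change is pulled toward zero further assumes that raters draw on the whole recall period. The 74% figure rests on uniform visit timing and 123 days of follow-up, and ranges from 100% at 91 days to about 50% at 183 days.

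A reader might infer that the off-treatment functional results are invalid throughout, or that a conclusion of the trial is at risk. The documents do not support either reading. Later assessments are clean, the on-treatment analysis excludes measurements after discontinuation, and the affected output is one descriptive table for an other secondary endpoint. This is a minor correction that is worth making.

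**What to change.** In SAP 5.4.2, state that the off-treatment ADCS-ADL-PI summary, for both subject- and informant-reported scores and including End point (Off-Trt), uses only assessments at least 3 months after the last dose. Define this as 91 days, which is off-treatment Analysis Day 92 or later. Show earlier off-treatment assessments in a separate, flagged display noting that their recall overlaps treatment. If the sponsor prefers to treat the two scales differently, the SAP should say why.

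This takes a sentence or two and one extra display, with no new data. The real cost is a small clean summary: on the model above, about 26% of scheduled off-treatment scores at 123 days of follow-up, none at 91 days and about half at 183 days. No record is lost, because the overlapping scores remain visible under an accurate label.
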